6.5. Analysis of safety

6.5.1. Analysis of safety planned in the protocol

The safety analysis will be based on the ES (also called TVC).

All analyses will be based on the ‘as treated’ analysis set.

Safety analysis will be descriptive, no inference and formal statistical comparison is planned for the safety data.

Safety reporting period differs depending on safety endpoints. [Table 4](#) shows the overview of the safety reporting

CONFIDENTIAL

207489 (NTHI MCAT-002)

Statistical Analysis Plan Amendment 2 FDA Final Draft

Table 4 Reporting periods for collecting safety information

Event	Screening Visit*	Visit 1	6 d post	29 d	Visit 3	6 d post	29 d	6 m post	Study	
		Dose 1	Dose 1	post Dose 1	Dose 2	Dose 2	post Dose 2	Dose 2	Concl	
Timepoint		Day 1	Day 7	Day 30		Day 61	Day 67	Day 90	Day 241	Day 451
Solicited local and general AEs										
Unsolicited AEs										
AEs/SAEs leading to withdrawal from the study										
SAEs										
SAEs related to study participation or concurrent GSK medication/vaccine										
Pregnancies										
plMDs										
Intercurrent medical conditions										

* i.e. consent obtained.

The double-bordered lines indicate timings of vaccination.

AE = adverse event; SAE = Severe adverse event; GSK = GlaxoSmithKline; plMD = potential immune mediated diseases

6.5.1.1. Solicited Local and General Adverse Events:

The following local AE will be solicited for 7 days after each vaccination:

CONFIDENTIAL

207489 (NTHI MCAT-002)

Statistical Analysis Plan Amendment 2 FDA Final Draft

Table 5 Solicited local adverse events:

Local AE	Grading	Collection period
at injection site	0: None 1: Mild 2: Moderate 3: Severe	Day 1-Day 7 Day 61-Day 67
Redness at injection site	0: < 20 mm diameter 1: ≥ 20 mm to ≤ 50 mm diameter 2: > 50 mm to ≤ 100 mm diameter 3: > 100 mm diameter	Day 1-Day 7 Day 61-Day 67
Swelling at injection site	0: < 20 mm diameter 1: ≥ 20 mm to ≤ 50 mm diameter 2: > 50 mm to ≤ 100 mm diameter 3: > 100 mm diameter 0	Day 1-Day 7 Day 61-Day 67

The percentage of subjects with at least one local solicited AE reported in diary card within 7 days after each dose (Day 1-Day 7) will be tabulated together with the exact 95% CI. Similarly, the percentage of doses followed by at least one local solicited AE will be tabulated together with the exact 95% CIs within each group. The percentage of subject with grade 3 solicited AEs lasting for at least two days will be reported, for each group, by vaccination and overall.

The same tabulation will be done for grade 3 solicited local AEs.

The following general AE will be solicited for 7 days after each vaccination:

Table 6 Solicited general adverse events:

General AE	Grading	Collection period
Headache	0: None 1: Mild 2: Moderate 3: Severe	Day 1-Day 7 Day 61-Day 67
Fatigue	0: None 1: Mild 2: Moderate 3: Severe	Day 1-Day 7 Day 61-Day 67
Gastrointestinal symptoms (nausea, vomiting, diarrhoea and/or abdominal pain)	0: None 1: Mild 2: Moderate 3: Severe	Day 1-Day 7 Day 61-Day 67
Myalgia	0: None 1: Mild 2: Moderate 3: Severe	Day 1-Day 7 Day 61-Day 67
Chills	0: None 1: Mild 2: Moderate 3: Severe	Day 1-Day 7 Day 61-Day 67
Fever	0: < 37.5°C 1: 37.5°C to 37.9°C 2: 38.0°C to 38.9°C 3: ≥ 39.0°C	Day 1-Day 7 Day 61-Day 67

CONFIDENTIAL

207489 (NTHI MCAT-002)

Statistical Analysis Plan Amendment 2 FDA Final Draft

The percentage of subjects with at least one general solicited AE reported in diary card within 7 days after each dose (Day 1-Day 7) will be tabulated together with the exact 95% CI. Similarly, the percentage of doses followed by at least one general solicited AE will be tabulated together with the exact 95% CIs within each group.

The exact 95% CIs will be calculated assuming independence between doses

The same tabulation will be done for grade 3 solicited general AEs.

The percentage of subjects reporting each individual local and general solicited AEs during the solicited follow-up period (i.e., day of vaccination and six subsequent days after each vaccination) by grading will be tabulated with exact 95% CI after each dose and overall by group. The percentage of doses followed by each individual solicited local and general AE will be tabulated overall by group with exact 95% CIs [Clopper CJ, Pearson ES. 1934]

The exact 95% CIs will be calculated assuming independence between doses.

For fever (irrespective of route of measurement), additional analyses will be performed by 0.5°C increments:

- <36.0,
- 36.0 - 36.4
- 36.5 - 36.9
- 37.0 - 37.4
- 37.5 - 37.9
- 38.0 - 38.4
- 38.5 - 38.9
- 39.0 - 39.4
- 39.5 - 39.9
- $\geq 40.0^{\circ}\text{C}$

6.5.1.2. Unsolicited Adverse Events:

All the unsolicited adverse events occurring during the study, judged either as related or not related to vaccination by the investigator, will be recorded.

The original verbatim terms used by investigators to identify adverse events in the e-CRFs will be mapped to preferred terms using the MedDRA dictionary. The unsolicited adverse events will then be grouped by MedDRA preferred terms into frequency tables according to system organ class. Adverse events judged by the investigator as at least possibly related to study vaccine will be summarized by vaccine group, according to system organ class (SOC) and preferred term within SOC. When an unsolicited adverse event occurs more than once for a subject, the maximal severity and strongest relationship to the vaccine group will be counted.

CONFIDENTIAL

207489 (NTHI MCAT-002)

Statistical Analysis Plan Amendment 2 FDA Final Draft

The percentage of subjects/doses with at least one report of unsolicited AE classified by the Medical Dictionary for Regulatory Activities (MedDRA) during a 30-day follow-up period after each dose (Day 1 –Day 30) will be tabulated with exact 95% CI for each group. The same tabulation will be performed by severity, and for unsolicited AEs with a relationship to vaccination.

SAEs, death, pIMDs and AE leading to withdrawal reported during the entire study will be tabulated (from Day 1 until study termination) and listed.

In addition, SAEs related to study participation or concurrent GSK medication/vaccine reported from informed consent signed until entire study duration will be also listed.

This study foreseen two injections (i.e., two vaccinations) for each subject, and thus unsolicited AEs summary tables will be presented overall and by period of onset and will include frequency distributions of the different adverse events:

Number and percentage of subjects with the following AEs will be computed:

Onset between day 1 and Day 30 after each vaccination:

- Any AE after each vaccination (overall)
- Any AE after each vaccination, by vaccination
- By severity AE after each vaccination (overall)
- By AE severity after each vaccination, by vaccination
- Related unsolicited AEs after each vaccination (overall)
- Related unsolicited AEs after each vaccination by vaccination
- Related unsolicited AEs by severe after each vaccination (overall)
- Related unsolicited AEs by severe after each vaccination by vaccination
- Any medically attended unsolicited AE (overall).
- Any medically attended unsolicited AE, by vaccination

Onset between day 1 and Day 450 (study termination):

- Any serious adverse events (SAE) (overall).
- Any serious adverse events (SAE) by vaccination.
- Related SAE (overall).
- Any AE leading to death (overall).
- Any unsolicited AE leading to premature withdrawal from study (overall).
- Any potential immune mediated diseases (overall)
- Any potential immune mediated diseases by vaccination
- Any AE leading to hospitalization (overall).

CONFIDENTIAL

207489 (NTHI MCAT-002)

Statistical Analysis Plan Amendment 2 FDA Final Draft

Onset between Screening and Day 450 (study termination):

- Any SAE related to study participation (overall).

6.5.2. Additional considerations

For solicited symptoms, missing or unevaluable measurements will not be replaced. Therefore, the analysis of the solicited symptoms based on the TVC (also called ES) will include only subjects/doses with documented safety data (i.e., symptom screen/sheet completed).

Solicited adverse events continuing beyond day 7 will be followed until resolution (up to Day 30).

For the unsolicited symptoms and concomitant medications/ products/ vaccinations, all vaccinated subjects will be considered and subjects who miss reporting symptoms/concomitant medications/ products/ vaccinations will be treated as subjects without unsolicited symptoms or concomitant medications/ products/ vaccinations, respectively.

6.5.2.1. Exclusion of implausible solicited Adverse Event

Some local and general adverse events will be directly measured by the subject and will not be subject to a reconciliation process, even if they are biologically implausible. Therefore, these implausible measurements will be removed from the analysis but included in listings. Implausible measurements are summarized in the table below:

Table 7 Implausible Solicited Adverse Events

Parameter	Implausible measurements
Body temperature	$\leq 33^{\circ}\text{C}$ or $\geq 42^{\circ}\text{C}$
Redness	≥ 900 mm < 0 mm
Swelling	≥ 500 mm < 0 mm

6.5.2.2. Combined Solicited and Unsolicited Adverse Events

A summary of subjects with all combined solicited (regardless of their duration) and unsolicited adverse events will be provided. Solicited adverse events will be coded by MedDRA as per the following codes:

CONFIDENTIAL

207489 (NTHI MCAT-002)

Statistical Analysis Plan Amendment 2 FDA Final Draft

Table 8 MedDRA coding for solicited AE

Solicited symptom	PT term code	Corresponding PT decode
Pain	10022086	Injection site pain
Redness	10022061	Injection site erythema
Swelling	10053425	Injection site swelling
Headache	10019211	Headache
Fatigue	10016256	Fatigue
Gastrointestinal symptoms	10017944	Gastrointestinal disorder
Myalgia	10028411	Myalgia
Chills	10008531	Chills
Fever	10037660	Pyrexia

The following results will be tabulated:

The percentage of subjects with at least one **local type AE** (solicited and unsolicited), with at least **one general** adverse event (solicited and unsolicited) and with **any AE** during the solicited follow-up period, i.e., the day of vaccination and six subsequent days after each vaccination will be tabulated with exact 95% CI after each vaccine dose and overall. The same tabulation will be done for grade 3 AEs.

The percentage of doses followed by at least one **local AE** (solicited and unsolicited), by at least one **general AE** (solicited and unsolicited) and by **any type AE** will be tabulated, overall vaccination course, with exact 95% CI. The same tabulation will be done for grade 3 AEs.

For clintrial.gov and EudraCT posting purposes, a summary of combined solicited and unsolicited non-serious adverse events is requested by System Organ Class and preferred terms and according to occurrence of each event. For this purpose, the following additional analysis will be produced:

- The number of occurrences of non-serious solicited and unsolicited AE classified by the MedDRA Preferred Terms and reported up to 30 days after each vaccination.
- The number of occurrences of SAE classified by the MedDRA Preferred Terms and reported from first vaccination up to study conclusion.

6.5.2.3. Pregnancies:

In case of any pregnancy from visit 1 (first vaccination) up to entire study duration, pregnancy reports and outcomes will be reported.

CONFIDENTIAL

207489 (NTHI MCAT-002)

Statistical Analysis Plan Amendment 2 FDA Final Draft

6.5.2.4. Clinical Safety Laboratory Investigations

Haematology profile, including differential cell counts is performed only at visit 1, before vaccination, and it will be summarized as baseline characteristics (see section 6.1.2) via descriptive statistics. For each parameter: N, mean, median, SD, min and max will be computed and the frequencies of subjects with values above or higher normal ranges by treatment group.

6.5.2.5. Concomitant Medication

This analysis will consider all medications taken (and reported) for different purpose than COPD or AECOPD. The analysis of medications to treat COPD or AECOPD (standard of care and not standard of care) is described in section 6.6.2.

Medications will be coded using the GSKDRUG dictionary.

The frequencies and percentages of subjects starting/reporting concomitant medications within the 7-day follow-up period (day 1 – day 7), during the 30-day follow-up period (day 1 – day 30) post-vaccination and during the entire study period will be tabulated by vaccine group for each study dose and across doses.

6.6. Other Analysis**6.6.1. Microbiological assessment****6.6.1.1. Sputum sample collection and quality**Sputum sample collection

Patient sputum sample will be collected (as stable visit) at Day 1 (before vaccination) and at Day 91, Day 181, Day 271, Day 361 and Day 451 and at each AECOPD driven visit, where AECOPD is confirmed.

Within each vaccine group the percentage of patients at each study visit (stable visit) and AECOPD confirmed visit will be computed overall and by the method (i.e., spontaneous at study visit or spontaneous at patient's home, induced using 0.9% saline or induced using 3% saline).

The proportion of sputum samples obtained at overall and at each stable and AECOPD visits and positive for specific bacterial pathogens by bacteriological culture and PCR will be computed, by vaccine group.

Sputum sample quality

The quality of sputum is assessed via squamous cells count, neutrophils cells count and bacteria direct smear. These will be summarized at any sputum visit (stable) and at any AECOPD confirmed visit, via frequencies tables (i.e., frequencies of sputum samples per quality scores [see section 11.2.7 in Annex 1] within each vaccine group)

CONFIDENTIAL

207489 (NTHI MCAT-002)

Statistical Analysis Plan Amendment 2 FDA Final Draft

If more than 20% of sputum samples have bad quality the analyses of bacteriological efficacy endpoint and bacteriological load (via PCR and culture) will be repeated in the subset of sputum samples with good and moderate quality.

6.6.1.2. Sputum bacterial/viral results via qPCR

[figure not shown]
Identification and quantification of the, *H. influenzae* (*Hi*), *M. catarrhalis* (*Mcat*) and *S. pneumoniae* (*Pn*) bacteria on frozen sputum samples will be performed using quantitative PCR (qPCR).

Testing results will be released as copies/mL values from 0 copies/mL up to the highest value.

Positivity cut-off (LOD – limit of detection): Samples with results below the positivity cut-off are negative. Samples with results equal to or above the LOD (equal to 1561, 927 and 1161 Copies/mL for *Hi*, *Mcat* and *Pn* respectively) are positive.

Limits of quantification (Lower (LLOQ) and Upper (ULOQ)): Only samples with results between the LLOQ and ULOQ are quantifiable. Nevertheless, as it is not needed to work with precise value, samples with results above the ULOQ and below LLOQ will be included in the quantitative analysis.

Figure 2 Sputum sample positivity by qPCR

For the occurrence, presence, acquisition and apparition analysis a sample will be considered positive (to *Hi*, or *Mcat* or *Pn*) if the qPCR results \geq LOD.

Load analysis will be performed for *Hi*, *Mcat* and *Pn* considering sputum samples with qPCR load above or equal to (\geq) the LOD, including the values belonging to the “not quantifiable” zone that will be anyway released by the assay (between LOD and LOQ, greater than ULOQ).

Occurrence and load of *Hi* and/or *Mcat*.

For each vaccine group the following analysis will be presented for sputum sample analysed via PCR:

CONFIDENTIAL

207489 (NTHI MCAT-002)

Statistical Analysis Plan Amendment 2 FDA Final Draft

- Overall proportion of sputum samples positive for Hi and Mcat with associated 95% CIs before vaccination (Day 1) and at any stable visit (Day 91, Day 181, Day 271, Day 361, Day 451) Day 91, Day 181, Day 271, Day 361, Day 451 and at any AECOPD visit
- Proportion of patients with sputum samples positive for Hi and Mcat with associated 95% confidence intervals (CIs), at each stable visit and at each AECOPD visit confirming acute exacerbation
- Summary statistics (N, mean, SD, median, minimum and maximum) and 95% CIs for the Hi and Mcat load will be displayed at each stable visit and at each AECOPD visit.

For the overall proportion, estimate and confidence intervals will be computed using a Generalized Estimating Equations (GEE) model assuming a binomial distribution for the response variable with logit as link function and a compound symmetry correlation matrix (exchangeable structure) to account for the within-patient correlations [Liang, 1986] and the following SAS code will be applied for stable visits, AECOPD visits separately and for Hi and Mcat bacteria:

```

PROC GENMOD data=<dataset> descending;
CLASS pid trt;
BY bacteria;
MODEL sp_positive = trt / dist = bin LINK = logit lrci ;
REPEATED subject=pid/ type=exch PRINTMLE;
ODS OUTPUT ParameterEstimates=out_parm ClassLevels=Class;
RUN;

DATA result;
SET out_parm(where=(parameter='Intercept') drop=ChiSq ProbChiSq DF);
format percent LL UL percent8.1;
Percent=exp(estimate) / (1+exp(estimate));
LL=exp(LowerLRCL) / (1+exp(LowerLRCL));
UL=exp(UpperLRCL) / (1+exp(UpperLRCL));
unit=_N_;
RUN;

```

where:

pid: patient id

trt= treatment arm;

sp_positive=sputum sample positive to bacteria (Hi or Mcat)

Acquisition and apparition of Hi and Mcat

The following definitions will be used (see Section 11.2.7 for further details):

Acquisition: The first time a bacterium is detected in the sputum of a patient over the course of the study visits (a positive status at the visit considered as baseline excludes a subject from this analysis).

Apparition: Detection of a bacterium in the sputum of a patient taken during a study visit which was not detected in the sputum taken during the previous visit

CONFIDENTIAL

207489 (NTHI MCAT-002)

Statistical Analysis Plan Amendment 2 FDA Final Draft

The following analyses will be performed for Hi (alone or with other bacteria), Mcat (alone or with other bacteria) and either Hi or Mcat:

- Percentages of subjects with acquisition for each treatment group and risk ratio between groups, considering both Day 1 and Day 91 as baseline.
- Percentages of subjects with apparition for each treatment group and risk ratio between groups, considering Day 1 as baseline.
- Percentages of subjects with acquisition at AECOPD visit for each treatment group and risk ratio between groups, considering both Day 1 and Day 91 as baseline.
- Percentages of subjects with apparition at AECOPD visit (when negative at previous stable visit) for each treatment group and risk ratio between groups, considering Day 1 as baseline
- Frequency table for apparition (number of apparitions for each subject from Day 1), by treatment groups.

Other bacteriological/viral pathogens

In addition to proportion of sputum positive to Hi (*Haemophilus influenza*) and Mcat (*Moraxella catarrhalis*) also the proportion of sputum samples obtained from PCR at pre-vaccination (Day 1), at Day 91, Day 181, Day 271, Day 361, Day 451 and at any AECOPD visit that are positive for specific bacteria (such as *S. pneumoniae*, *S. aureus*, *P. aeruginosa* and *Streptococcus pyogenes* [*S. pyogenes*]) and virus (such as *respiratory syncytial virus*, *parainfluenza virus*, *enterovirus/ rhinovirus*, *metapneumovirus*, *influenza virus*, *adenovirus*, *bocavirus* and *coronavirus*) will be presented together with the 95% CIs.

For the *S. pneumonia* and Rhinovirus summary statistics (N, mean, SD, median, minimum and maximum) and 95% CIs for the load will also be tabulated.

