2. STUDY DESIGN

Figure 1 Study design overview

S = Screening Visit; V = Visit; PC = Phone contact; D = Day; FU = Follow-up; BS (1) = blood sample for humoral immunogenicity; BS (2) = blood sample for cell-mediated immunogenicity (CMI), this blood sample will only be collected from a sub-cohort of subjects; BS (3) blood sample for biomarkers; SP = sputum sample

The allowed maximum interval between Screening Visit and Visit 1 is 29 days. If a delay occurs for an eligible subject so that the interval exceeds 29 days, some study procedures performed during the Screening Visit needs to be repeated within 7 days (see Table 6 of the protocol for more details).

* An AECOPD visit should be scheduled as soon as possible after the onset of AECOPD symptoms (max 96 hours after and, if applicable, preferably before starting treatment with antibiotics) During this visit blood and sputum samples will be collected. In addition, follow-up phone call(s) and/or visit(s) will take place to determine the end of the AECOPD. These contacts will take place at least every 2 weeks until the AECOPD is resolved.

Investigational vaccine and placebo will be administered in addition to standard of care.

- **Experimental design:** Phase IIB, randomised, observer-blind, placebo-controlled, multi-centric study with two parallel groups.
- **Duration of the study:** for each subject enrolled, the study will last approximately 15 months from Visit 1 up to study completion (Visit 8).
 - Epoch 001: Screening Visit (Day -28 to Day -1).
 - Epoch 002 : Primary starting at Visit 1 (Day 1) and ending at Visit 8 (Day 451).
- **Primary completion Date (PCD):** Last Subject Last Visit (LSLV) from Visit 8 (Day 451) or last visit/contact of Epoch 002.
- **Study groups:**
 - **10-10-3-AS:** Approximately 300 subjects receiving two doses of the AS01_E-adjuvanted GSK Biologicals' NTHi-Mcat investigational vaccine containing 10 µg of PD, 10 µg of PE-PilA, and 3.3 µg of UspA2.
 - **CONTROL:** Approximately 300 subjects receiving two doses of placebo (PBS).

CONFIDENTIAL

207489 (NTHI MCAT-002)

Statistical Analysis Plan Amendment 2 FDA Final Draft

The following group names will be used for the statistical analysis

Table 1 Study groups and epochs foreseen in the study

Group order in tables	Number of subjects	Group label in tables	Group definition for footnote
1	~300	10-10-3-AS	2 doses of AS01E-adjuvanted NTHI/Mcat vaccine containing 10 mcg of PD, PE-PiA and 3 mcg of UspA2

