3.3. Tertiary objectives

- To evaluate the effect of the investigational vaccine on the presence, acquisition/apparition and load of NTHi and/or Mcat at stable visits and AECOPD by PCR.
- To evaluate the effect of the investigational vaccine on the presence, acquisition/apparition and load of NTHi and/or Mcat at stable visits and AECOPD in a subset of sputum samples by culture.
- To explore the efficacy of the investigational vaccine as compared to placebo with respect to the rate of all AECOPDs and by severity (i.e. mild, moderate or severe) associated with NTHi and/or Mcat detected in a subset of sputum samples by culture.
- To explore the impact of the investigational vaccine on health-related quality of life (HRQOL).
- To explore the impact of the investigational vaccine on use of medication for COPD and Healthcare Resource Utilisation.
- To explore the impact of the investigational vaccine on lung function.
- To describe selected biomarkers in stable COPD and during AECOPD.
- To explore the T helper profile of the PD-, PE-, PilA-, UspA2-specific CD4⁺/ CD8⁺ T cell responses.

CONFIDENTIAL

207489 (NTHI MCAT-002)

Statistical Analysis Plan Amendment 2 FDA Final Draft

- To collect blood and sputum samples for assay development, for lung microbiome analysis, to explore the level of inflammation (into the lung) and/ or for additional evaluation of the immune responses to the investigational vaccine and to other potential pathogens involved in AECOPD.
- To explore the data for an immune correlate of protection.

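### Presence of Hi and Mcat at stable visits gets no between-arm estimate, although a tertiary objective asks for the vaccine's effect on it; the Day 1 sample already collected could sharpen one

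*SAP*

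**What the plan says.** All references are to SAP Amendment 2, the current version.

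- **Objective (3.3):** "To evaluate the effect of the investigational vaccine on the presence, acquisition/apparition and load of NTHi and/or Mcat at stable visits" and at AECOPD, by PCR, with a parallel objective for culture.
- **Planned output (6.6.1.2):** for each group, an overall proportion of positive samples, and by visit "Proportion of patients with sputum samples positive for Hi and Mcat with associated 95% confidence intervals".
- **Model (6.6.1.2):** "For the overall proportion, estimate and confidence intervals will be computed using a Generalized Estimating Equations (GEE) model", with "a compound symmetry correlation matrix (exchangeable structure) to account for the within-patient correlations". The code fits "MODEL sp_positive = trt / dist = bin LINK = logit lrci" by bacterium, separately for stable and AECOPD visits.
- **What is kept:** the next data step reads "SET out_parm(where=(parameter='Intercept') drop=ChiSq ProbChiSq DF" and back-transforms that one parameter to a percentage with limits.
- **Between-arm estimates under the same objective:** risk ratios for acquisition and apparition only.
- **Culture (6.6.1.3):** proportions within each group, by the PCR method.
- **Baseline:** sputum is taken at "Day 1 (before vaccination) and at Day 91, Day 181, Day 271, Day 361 and Day 451" (6.6.1.1). Carriage is not among the four minimisation factors in 11.3. The SAP adjusts for baseline in the antibody ANCOVA (6.4.1) and the EXACT-PRO ANCOVA (6.6.2).

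**The concern.** The objective asks for an effect on presence, and the plan delivers none. The treatment coefficient is fitted and then dropped. Under GENMOD's default class coding, with no BY statement for treatment, the retained intercept is the logit for the reference arm, so the code as written does not even return the two arm proportions that the text promises. Readers would be left to compare two percentages by eye, although section 7 sets a p-value reference of 0.1 for tertiary comparisons. Section 6.3.1.2, under its inferential heading, also gives only sample proportions with exact intervals.

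Once a contrast is reported, a second choice matters. Each subject's own pre-vaccination status is in the database and is likely to predict later carriage. Leaving it out would give up precision that costs no new data.

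**Working it through.** **The plan's own figure.** There is none to reproduce: the SAP states no prevalence, within-patient correlation, power or target difference for presence.

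**Inputs from the SAP.** About 300 subjects per arm (section 2); one pre-vaccination and k = 5 later stable samples (6.6.1.1); reference level 0.10 (section 7).

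**Assumptions, not in the SAP.** Prevalence, between-visit correlation ρ, a 20% relative reduction in carriage for the power figures, and complete sputum data.

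**Closed form.** With equal variances and exchangeable correlation ρ, the mean of k later visits has variance σ²(1 + (k−1)ρ)/k, and its covariance with Day 1 status is ρσ². The share of variance explained by Day 1 status is

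R² = kρ² / (1 + (k−1)ρ) = 5ρ² / (1 + 4ρ),

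and the ratio of adjusted to unadjusted standard error is √(1 − R²).

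- ρ = 0.14: 5 × 0.0196 / 1.56 = 0.063
- ρ = 0.52: 5 × 0.2704 / 3.08 = 0.439

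A random-intercept logistic simulation (SD 1, 2 and 3; prevalence 0.2 and 0.3; ρ from 0.14 to 0.52) gave R² of 0.06-0.08, 0.25-0.28 and 0.42-0.45, in agreement. This is the source of the 6-45% range.

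**Simulation of the contrast.** Beta-binomial carriage, 300 per arm, 1,500 replicates, risk difference over five visits without and with Day 1 status:

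| ρ | R² (closed form) | SE ratio (closed form) | SE ratio, simulated, at prevalence 0.15 / 0.30 / 0.45 | Power at 0.10, prevalence 0.30 |
|---|---|---|---|---|
| 0.1 | 0.036 | 0.982 | 0.989 / 0.988 / 0.989 | 0.95 → 0.95 |
| 0.2 | 0.111 | 0.943 | 0.955 / 0.954 / 0.958 | 0.88 → 0.91 |
| 0.3 | 0.205 | 0.892 | 0.898 / 0.905 / 0.906 | 0.82 → 0.89 |
| 0.5 | 0.417 | 0.764 | 0.797 / 0.776 / 0.808 | 0.74 → 0.90 |

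**Visit as a covariate.** In the one logit-GEE setting completed (prevalence 0.15, ρ = 0.2), adding visit alone gave an SE ratio of 0.997, which is almost no gain.

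**Odds ratio.** In a logit GEE with 300 per arm and five visits, adding Day 1 status moved the standard error of the log odds ratio from 0.108 to 0.107, 0.141 to 0.139 and 0.156 to 0.159 at random-intercept SD 1, 2 and 3. The estimate moved away from zero instead (−0.27 to −0.30 at SD 2; −0.19 to −0.27 at SD 3), because the adjusted odds ratio is conditional on Day 1 status. Power rises, but the variance reduction above belongs to the risk difference.

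**Why Day 1 must not be an outcome.** Section 6.6.1.1 groups the Day 1 sample with the stable visits, while 6.6.1.2 lists it apart. If it were pooled as a sixth visit, the arm difference would shrink to 5/6: at prevalence 0.30 with a 20% reduction, from −0.060 to −0.050.

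**The case against.** The strongest reply is that the model does what it is declared to do: it summarises an overall proportion with allowance for clustering. The objective is tertiary, and section 7 calls such comparisons exploratory. Day 1 proportions are shown separately, so an imbalance would be visible. Acquisition, with risk ratios among subjects negative at Day 1 or Day 91, is already a between-arm contrast restricted by baseline carriage.

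Much of this stands, and it rules out several stronger readings:

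- **That the planned analysis is imprecise.** It is descriptive. The precision figures concern a contrast that the plan does not contain.
- **That a Day 1 imbalance would be mixed into the vaccine effect as bias.** Under randomisation the unadjusted comparison is unbiased, and chance imbalance is part of its sampling error.
- **That the whole objective lacks an arm comparison.** Acquisition and apparition have one. The gap is presence.
- **That omitting visit costs precision.** The check found almost no cost.

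What does not stand is that description is enough. The same list of objectives says describe where it means describe (biomarkers), and evaluate the effect here. Acquisition excludes subjects positive at baseline, and apparition requires a negative previous visit, so neither measures continued carriage in subjects already positive. Section 8 also places PCR presence and load in the first-priority study report without naming acquisition or apparition there.

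**Conclusion.** The point holds as a gap in a tertiary analysis. For presence of Hi and Mcat the plan reports no between-arm effect, and its code returns only one arm's proportion. This does not depend on any assumption about carriage.

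The benefit of using Day 1 status does. At prevalence of 20-30% and ρ of about 0.14 to 0.52, it lowers the variance of the risk difference by about 6-45%; at ρ = 0.1 the reduction is under 4%. The SAP offers nothing to narrow that range. A reader might carry the same percentage over to an odds ratio, but the simulations show its standard error hardly moving. Primary and secondary efficacy conclusions are untouched.

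**What to change.** In section 6.6.1.2, for stable visits Day 91 to Day 451 with Day 1 excluded as an outcome:

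1. Fit the GEE with treatment and Day 1 status for the same bacterium. Give subjects with no Day 1 result their own category. Visit may be added as a design term, with little gain expected.
2. Report the between-arm standardised risk difference for Hi, Mcat and either, with a 95% CI that allows for within-patient correlation, such as a subject-level bootstrap or a delta method on the robust covariance.
3. Label any odds ratio as conditional on Day 1 status.
4. Keep the proportions as description, and correct the code so that both arms are returned. The limits it now reads are likelihood-ratio limits, which come from the independence fit and not the GEE; new code should not inherit this.
5. In the culture subset (6.6.1.3), do the same with Day 1 culture status.

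The cost is one or two model terms, the standardisation and interval step, and an extra table row per bacterium. No new data are needed.
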